#### **Covariates for stratification:**

Covariates for stratification will vary across objectives and will include:

- Age group:
   10-17, 18-34, 35-49, 50-64, +65 years.
- Indication:

Non-HRT vs. HRT. Indication will be assessed using age as a proxy (non-HRT in women aged 10-49 years, HRT in women aged >50 years).

- Dose:
  - High- vs low- dose, for NOMAC or CMA only. For NOMAC, high doses will include amounts from 3.75mg to 5mg. For CMA, high doses will include amounts from 5mg to 10mg. Low doses will be any amounts less than those specified.
- WHO 5th ATC level codes:
  - For NOMAC or CMA only, if counts allow. For NOMAC codes included will be: G03AA14, G03DB04, G03FB12. For CMA, codes included will be: G03AA15, G03AB07, G03DB06, G03FB03.
- Time period:
  - Preintervention: from start date to October 2022; Postintervention: from February 2023 to study end.

See below which covariates apply according to each objective.

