Several factors have been identified to potentially influence the power to estimate the impact of the intervention, including the total number of time points, the average sample size per time point, the expected effect size, the location of intervention in time series or the impact model used.(20) In previous studies, ITS have been found to have more than 80% power to detect effect sizes of 1.0 or greater in a range of situations with 24 or more points, depending on the degree of autocorrelation and the impact model used.(21) Unbalanced designs (i.e. unequal number of time points before and after the intervention) have been found to have less power than balanced designs.(20, 21) As the intervention is located at the end of the time series, we will delay the study period start to balance the number of observations for Objective 6 and to ensure a more recent contrafactual for comparison (see "8.8 Analysis").

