#### Objective 6:

The impact of the restrictions of use will be estimated using an ITS. This analysis will be restricted to NOMAC and CMA (assessed separately) and will be informed by results of the main analysis obtained as part of objective 1 (no meningioma restriction). For NOMAC, the intervention taken place in 2018 will also be assessed.

Time series will be assessed using segmented regression. Monthly incident counts of patients prescribed with NOMAC or CMA will be modelled using a Poisson regression model. Quasi-Poisson models will be considered in the presence of overdispersion. The effect size of the intervention will be estimated using risk ratios (RR).

The assumption of linearity will be assessed by visually inspecting the data and residuals, as well as through statistical goodness-of-fit tests. Autocorrelation will be assessed by examining the plot of residuals and the partial autocorrelation function and conducting statistical tests where possible. If seasonality is detected, it will be controlled for by including variables representing them in the regression model. If the trends are not (or cannot be transformed to be linear) or in the presence of residual autocorrelation, ITS will not be conducted due to the complexity of predicting the counterfactual and to disentangle the intervention effects.(23)

Authors: [name], [name], [name], [name], [name]

Version: V4.0

Dissemination level: Public

The impact model of the intervention (i.e. how we expect the intervention has impacted the outcome) is anticipated to show an abrupt change in the level and a gradual change in the gradient of the trend (step and slope change). Potential impact models will be further discussed and agreed with EMA and defined a priori.(23, 24)

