The amount of pre-intervention data to include for this analysis will be based on defining a valid counterfactual for the ITS analysis. Given the large amount data (12 years before the intervention), the range of pre-intervention data will be restricted to ensure the validity of the comparison (i.e. historical trends might differ from the most recent ones). To analyse the impact of restrictions adopted in 2022, analysis will be conducted using data from 1st January 2021 onwards. For NOMAC, the intervention adopted in 2018 will be assessed using data from 1st January 2017 onwards. Methodological considerations will be evaluated based on the visual assessment of the trends. This may include adjustments on the amount of pre-intervention data or the frequency of data points, if deemed necessary to support the analysis.

Results will be reported overall and stratified by dose (high- vs. low- dose products) and indication (non-HRT vs. HRT).

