#### **Databases:**

In IQVIA LPD Belgium and IQVIA DA Germany, the observation period of the patients in these databases is calculated based on the last visit, observation or interaction of the patient with the health care system. This methodology impacts the individuals considered "at risk" for the different medicines of interest of the study (i.e., the individuals included in the denominator populations) during the latest months of available data from the latest data lock, where healthy and/or non-frequent users of the health care system will not be considered active. Consequently, the denominators that will be used to calculate the incident use of drugs in the population may present an artefactual decrease whilst the incident users will remain, incrementing the incidence and prevalence ratios. The presence of these artefacts will be considered when interpreting the results. However, this is likely to affect the amount of follow up available for the study. We expect that the data from the last 6 months may not accurately reflect actual figures of use and, therefore, will be excluded from the analysis for Objective 1 and 6.

Regarding the study period, NAJS will provide data from 2017 onwards only, as prior data might include information on duplicated patients. IQVIA LPD Belgium will provide data from 2012 onwards.

Since information on drug exposure end dates is unavailable in NAJS, treatment duration will not be inferred directly from the start and end dates of drug exposure. Instead, we will infer the treatment period using only the drug exposure start dates, assuming continuous drug exposure between consecutive start dates, if separated by less than 90 days. To account for the final prescription, we apply a 30-day window following the last recorded drug start date. This approach might lead to some uncertainty regarding the exact duration or cumulative dose prescribed.

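### On the listed data locks, the 2022 interrupted time series has 22 months before the intervention but only 2, 5 and 9 after it, so the balance stated in 8.7 is not achieved and the German post-intervention segment is fitted exactly

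*Protocol*

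**What the plan says.** Section 8.7 (Study size) reports no sample-size calculation. It cites simulation work with power above 80% for effects of at least 1.0 in a range of settings once a series has 24 points. It warns that unequal segments lose power and states that "we will delay the study period start to balance the number of observations for Objective 6", with a more recent counterfactual as a second aim.

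The dates that decide the matter stand elsewhere:

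- Section 8.8, Objective 6: "To analyse the impact of restrictions adopted in 2022, analysis will be conducted using data from" 1 January 2021.
- Section 8.6.3: "Preintervention: from start date to October 2022". The post period starts in February 2023, and the months between are left out of Objective 6.
- Table 3: the locks are 30-09-2023 (Germany), 31-12-2023 (Belgium) and 17-11-2023 (NAJS).
- Section 11, Databases, in a paragraph on the two IQVIA sources: "We expect that the data from the last 6 months may not accurately reflect actual figures of use and, therefore, will be excluded" for Objectives 1 and 6.
- Sections 8.4 and 8.8: Objective 6 has the follow-up of Objective 1, which uses complete calendar months only.

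The anticipated impact model is "an abrupt change in the level and a gradual change in the gradient of the trend (step and slope change". On the outcome scale, "Monthly incident counts of patients prescribed with NOMAC or CMA will be modelled using a Poisson regression model", whereas Table 11 names incidence rates as the Objective 6 outcome. For the earlier action, "For NOMAC, the intervention adopted in 2018 will be assessed using data from" 1 January 2017 onwards, with no end date.

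**The concern.** The protocol never adds up these dates. Added up, they contradict the property that 8.7 ascribes to the design, and the post segments are very short for a model with both a step and a slope change. Germany, the largest source (16.8k NOMAC and 173.9k CMA users in the feasibility counts), has the shortest one.

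Objective 6 is the only model-based estimate of the effect of the 2022 measures. Section 8.8 lets the analysis go ahead only if linearity and residual autocorrelation look acceptable. If the post segment is fitted exactly, those checks see the pre-period alone. Germany could pass them and report a slope change that is no more than the difference between two months.

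Two further statements in the same specification affect what the risk ratios mean: counts are modelled while rates are named as the outcome, and the 2018 series has no end.

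**Working it through.** **1. Months available.** The pre-period is January 2021 to October 2022: 12 + 10 = 22 months. The post period starts in February 2023.

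| Database | Lock | Last usable month | Post months | Total | Pre:post |
|---|---|---|---|---|---|
| Germany | 30-09-2023 | March 2023 (lock less 6 months) | 2 | 24 | 11.0 |
| Belgium | 31-12-2023 | June 2023 (lock less 6 months) | 5 | 27 | 4.4 |
| NAJS | 17-11-2023 | October 2023 (complete months) | 9 | 31 | 2.4 |
| NAJS, if the six-month cut applied | 17-11-2023 | April 2023 | 3 | 25 | 7.3 |

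Without the six-month exclusion, Germany would have 8 post months and Belgium 11, which is still unbalanced.

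**2. The cited benchmark.** It cannot be reproduced, because the protocol gives neither its effect-size definition, nor its autocorrelation, nor its impact model. Germany's total is exactly 24 points, but a 22/2 split gives no reassurance.

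**3. Precision of the slope change.** This is an illustration by ordinary least squares with independent errors, in units of the residual SD. The model has an intercept, trend, step and slope change. With n equally spaced months in a segment, Sxx = n(n² − 1)/12, and

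SE(slope change) = √(1/Sxx,pre + 1/Sxx,post).

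Sxx,pre = 22 × 483/12 = 885.5, so 1/Sxx,pre = 0.0011.

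- Germany: Sxx,post = 2 × 3/12 = 0.5; SE = √(0.0011 + 2) = 1.41.
- Belgium: Sxx,post = 5 × 24/12 = 10; SE = √(0.0011 + 0.1) = 0.32.
- NAJS: Sxx,post = 9 × 80/12 = 60; SE = √(0.0011 + 0.0167) = 0.13.
- NAJS with 3 months: Sxx,post = 3 × 8/12 = 2; SE = √(0.0011 + 0.5) = 0.71.
- For comparison, 12/12: Sxx = 143 in each segment; SE = √(2/143) = 0.12. For 22/22: √(2/885.5) = 0.048.

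**4. What can be checked in Germany.** The model has 4 parameters on 24 points, so 20 residual degrees of freedom. All 20 come from the pre-period (22 − 2). Both post months have leverage 1.0. A simulated Poisson fit at 22/2 gave post residuals of zero and a deviance equal to that of the pre-period fitted alone (10.99 in both).

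**5. Counts or rates.** If counts were fitted without person-time, a constant daily rate would still rise by 31/28 = 1.107 from February to March. In Germany that would appear as a post slope of +10.7% per month.

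**6. The 2018 NOMAC series.** Section 8.6.3 sets its transition at October 2018 to January 2019, so the post segment starts in February 2019. Read literally, it runs through the pandemic, the 2020 action and the 2022 measures. Section 11 sets the 2020 action aside because the pandemic could bias its estimate. NAJS supplies data from 2017 and 365 days of history are required, so its first usable month is about January 2018. That leaves January to September 2018, about 9 pre months.

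**The case against.** The best defence is that the counts are provisional. Table 3 labels the locks as those of the last update, the study period runs to the end of data availability, and execution is planned for March/April 2025. The post window for Objective 2 reaches January 2024, beyond every listed lock. This stands: a later release would add months. Balance would still not follow. Twenty-two post months would run to November 2024, which with the six-month cut needs an IQVIA lock at the end of May 2025, after the planned execution.

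The protocol also keeps some freedom. Impact models are to be agreed with EMA, and pre-period length or data frequency may change after the trends are seen. Section 11 admits that follow-up will be affected and that long-term effects may be missed. None of this adds post months or sets a minimum number of them.

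In context, balancing can be read as trimming twelve years of history. That softens the sentence but does not make it correct.

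Four stronger readings are tempting, and the documents do not support them:

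- *The German model is saturated.* It keeps 20 residual degrees of freedom; only its post segment is saturated.
- *Imbalance destroys power for a level change.* With the same three-month gap, a 12/12 series has a level-change SE of 1.00, against 1.13 in Germany, 0.94 in Belgium and 0.81 in NAJS. Two of the three unbalanced series do better.
- *Section 8.7 claims more than 80% power.* It cites a qualified benchmark and says that no calculation was made.
- *Objective 6 is the only measure of effectiveness.* Table 10 and the Objective 2-5 text also use pre/post standardised mean differences for this.

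A person-time offset is a detail that an analysis plan could supply, and Objective 1 already computes person-time. It is a matter of reconciling wording.

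**Conclusion.** The point holds. On the Table 3 locks the series is 22:2, 22:5 and 22:9, so the balance stated in 8.7 is not achieved in any database. The harm lies in the slope change: severe in Germany (SE about 1.4 residual SDs per month, roughly twelve times that of a 12/12 series), appreciable in Belgium (0.32), and small in NAJS at 9 months (0.13). In Germany the checks that decide whether the analysis is run cannot test the post period at all.

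This rests on the listed locks, on the six-month exclusion covering only the IQVIA databases (the natural reading of section 11), and, for the standard errors, on independent errors of equal variance. Autocorrelation or Poisson variation would change the sizes but not the month counts or the exact fit. The open-ended 2018 series and the count/rate wording are secondary faults in the same specification.

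**What to change.** 1. In 8.7, replace the balance sentence with the expected pre and post months per database, updated to the data release actually analysed. Say whether the six-month exclusion applies to NAJS.
2. Fix, before any trend is viewed, the minimum number of usable post months for estimating a slope change. Below it, fit a level change only, or show the Objective 1 rates descriptively. The documents give no basis for a particular threshold, so agree it with EMA together with the impact model.
3. State that the Poisson model uses a log person-time offset, in line with the incidence-rate outcome in Table 11.
4. End the 2018 NOMAC series before COVID-19 and the 2020 and 2022 actions, and note that NAJS has only about 9 pre months for it.

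The cost is protocol wording and small changes to model code, with no new data. The downside is that Germany may have no slope estimate, or no interrupted time series, on the current lock.

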## 8.8 Analysis

The type of analysis by study type is fixed as can be observed from **Table 10**.

**Table 10.** Description of study types and type of analysis.

Study type	Study classification	Type of analysis
Population Level DUS	Off-the-shelf	

Population-based incidence rates

Population-based prevalence of use of a drug/drug class

Patient Level DUS	Off-the-shelf	
 
Characterisation of patient-level features
 
Frequency and % of indication/s
 
Estimation of minimum, p25, median, p75, and maximum initially prescribed or dispensed dose/strength
 
Estimation of minimum, p25, median, p75, and maximum treatment duration
 

Trend analyses and RMM effectiveness	Complex	
 
Incidence and prevalence rate/s of drug/s use over time
 
For patient-level analyses, standardised mean differences of each of the covariates for the comparison between new drug user/s in the pre-RMM vs post-RMM period will be obtained
 
Measures of patient-level DUS (descriptives of treatment duration) will be provided
 

The analyses that will be performed for each objective are detailed below. A summary can be found in **Table 11.** 

P3-C3-006 St	udy Protocol
--------------	--------------

Version: V4.0

Dissemination level: Public

#### Objective 1:

Monthly incidence rates with 95% CI will be calculated as the number of new prescriptions per 100,000 person-years of the population at risk during the study period. Each of the drug classes and progestogens of interest will be treated as a separate outcome (see "8.6.2. Outcomes" for more information).

A washout window of 365 days will be applied after each treatment episode. Therefore, participants with an outcome record will not contribute time to the study during the 365 days following the end of each treatment episode. Participants will be able to re-enter the study after the washout window has passed. This washout will be applied for each outcome separately and will be specific to the drug class or progestogen of interest being under study. Please note that a treatment episode might consist of several consecutive prescriptions (see "8.6. Variables" for more information).

Period prevalence with 95% CI will be calculated as the proportion of study participants who were prescribed with an outcome medication monthly.

Objective 1 will only be conducted for complete calendar months observed in the database (e.g., if the end of available data is 15th of June 2023, only data up to 31st May 2023 will be considered). Results will be reported overall and stratified by study period (pre- vs. postintervention), age group (10-17, 18-34, 35-49, 50-64, +65), dose (high- vs. low- dose products, for NOMAC and CMA only), indication (non-HRT vs. HRT) and WHO 5th ATC level codes (if counts allow).

A subgroup analysis will be conducted restricting the study population to those individuals with a prior history of meningioma. All individuals within the study population with a documented history of meningioma will be included, irrespective of the time elapsed since their diagnosis, and will contribute time to the analysis from the date of diagnosis. Given the limited number of feasibility counts for this condition, results will only be reported overall and by calendar years. Please see the limitation section for further details.

## Objective 2:

Treatment duration will be reported for the first prescribed treatment. Duration will be derived from the start and end of the prescription.

Cumulative dose will be calculated considering all treatments containing NOMAC or CMA recorded during the study period. If two eras with different doses are separated by less than 30 days, the time between the two eras will be considered as exposed by the first era (Figure 1, first row). If two eras start at the same date, the overlapping period will be considered exposed by both.

[figure not shown]

Figure 1. Gap era joint mode

Cumulative dose and treatment duration will be calculated for all treatments initiated during the study period and occurring over one year before and after the intervention to compare time periods of equal duration. The pre-intervention period for comparison will span from October 2021 to September 2022,

Authors: [name], [name], [name], [name], [name]

Version: V4.0

Dissemination level: Public

the year prior the request for PRAC to review current evidence on NOMAC and CMA. The post-intervention period for comparison will span from February 2023 to January 2024. For databases with less available data (see Table 3) we will limit the comparison to 6 months (post-intervention: February to July 2023; pre-intervention: February to July 2022). Time periods for comparison will cover the same calendar months in case seasonality is detected.

NOMAC and CMA will be assessed separately. Results will be reported overall and stratified by study period (pre- vs. postintervention) and indication at first use (non-HRT vs. HRT).

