## 8.4 Follow-up

For the population-level DUS (objective 1), study participants in the denominator population will start contributing person time on the latest of the following: 1) study start date (1st January 2010, or as defined according to the database), 2) date on which they turn 10 years old, 3) date at which they have a year of prior history recorded. Participants will stop contributing person time at the earliest date of the following: 1) end of available data in each of the data sources, 2) date at which their observation period ends (e.g. loss to follow-up, death).

For the patient-level DUS (objective 2 to 5), participants will be followed up from the day of incident prescription of medication (index date), until the earliest end of data availability, date at which their observation period ends (e.g. loss to follow-up, death), or 180 days after ending treatment (objective 5). For objective 2, 4 and 5, index date will be defined as the date of the first-ever prescription of NOMAC or CMA. For objective 3, this will be defined as the date of the first-ever prescription of any of the 6 drug classes of interest (see "8.6.2 Outcomes").

For objective 4, line of treatment will be assessed retrospectively by looking at prior records of alternative treatments, from the date of initiation of treatment with products containing NOMAC or CMA to start of the study period (1st January 2010, or as defined according to the database).

For objective 6, follow-up will be the same as that for objective 1.

Information on the operational definition of index date is described in **Table 4**. Please note that, for objectives 1 and 6, each drug class of interest will be assessed separately, with the washout window specific to the drug class being studied (e.g., when studying NOMAC, the washout window will be applied with respect to this substance only). For objective 3, the washout will be applied to all the drug classes of interest combined.

Authors: [name], [name], [name], [name], [name]

Version: V4.0

**Dissemination level:** Public

Table 4. Operational definition of time 0 (index date) and other primary time anchors.

Study population names	Time Anchor Description (e.g. time 0) 	Number of entries 	Type of entry	Washout window	Care Setting 	Code Type 	Incident with respect to

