# Appendix II: Relevant dates of the assessment of nomegestrol acetate and chlormadinone acetate.

Date	Procedure
10/2018	Adoption of CMDh position
1/12/2018	Transmission to the National Competent Authorities of the translation of the annexes to the position
30/01/2019	Implementation of the position by the Member States (submission of the variation by the Marketing Authorisation Holder)

CMDh= Coordination Group for Mutual Recognition and Decentralised Procedures-Human

Source: European Medicines Agency. Nomegestrol: CMDh Scientific conclusions and grounds for variation, amendments to the Product Information and timetable for the implementation - PSUSA/00002181/201801.

https://www.ema.europa.eu/en/medicines/psusa/psusa-00002181-201801

Date	Procedure
22/09/2021	Date of request for PRAC assessment by France
30/09/2021	Procedure start date
07/07/2022	PRAC recommendation date
01/09/2022	CHMP opinion date (endorsement of PRAC's assessment risk)
8/11/2022	DHPC dissemination date
28/11/2022	European Commission decision date
28/12/2022	Timeline for Marketing Authorisation Holders to implement changes

PRAC= Pharmacovigilance Risk Assessment Committee; CHMP = Committee for Medicinal Products for Human Use.

Source: European Medicines Agency. Nomegestrol and chlormadinone -referral.

https://www.ema.europa.eu/en/medicines/human/referrals/nomegestrol-chlormadinone

Authors: [name], [name], [name], [name], [name]

Version: V4.0

Dissemination level: Public

**Appendix III**: ENCePP checklist for study protocols

**Study title:** DARWIN EU® – Impact of risk minimisation measures related to the risk of meningioma in women using nomegestrol and chlormadinone

Sec	tion 1: Milestones	Yes	No	N/A	Section Number
1.1	Does the protocol specify timelines for				
	1.1.1 Start of data collection 				5, 8.2
	1.1.2 End of data collection 	$\boxtimes$			
	1.1.3 Progress report(s)			$\boxtimes$	
	1.1.4 Interim report(s)			$\boxtimes$	
	1.1.5 Registration in the EU PAS Register®	$\boxtimes$			
	1.1.6 Final report of study results.	$\boxtimes$			
Comr	nents:				
Sec	tion 2: Research question	Yes	No	N/A	Section Number
					Hullibei
2.1	Does the formulation of the research question and objectives clearly explain:	$\boxtimes$			Number
2.1	

objectives clearly explain:

2.1.1 Why the study is conducted? (e.g. to address an important public health concern, a risk identified in the risk

				7, 8.8

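### Objective 2 matches initiation windows but fixes no equal per-patient accrual period for cumulative dose, and its 12-month baseline label contradicts Appendix II

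*Protocol*

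**What the plan says.** **Accrual.** Section 8.8, Objective 2: "Cumulative dose will be calculated considering all treatments containing NOMAC or CMA recorded during the study period". Section 8.4 adds that "participants will be followed up from the day of incident prescription of medication (index date), until the earliest end of data availability", or until the observation period ends. The 180-day limit in that section is tied to Objective 5.

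**Windows.** "The pre-intervention period for comparison will span from October 2021 to September 2022", and "The post-intervention period for comparison will span from February 2023 to January 2024". Databases with less data use February-July 2022 against February-July 2023. Section 8.7 confirms that the windows select on when treatment starts.

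**Competing wording.** The study design paragraph of the abstract describes duration and cumulative dose as measured within a set period of 6 or 12 months. The matching list in section 8.1 omits this. The comparison sentence in section 8.8 can also be read as requiring treatment to fall inside the window.

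**Duration.** This covers the first prescribed treatment: "Duration will be derived from the start and end of the prescription". In NAJS, which has no end dates, section 11 infers episodes by "assuming continuous drug exposure between consecutive start dates, if separated by less than 90 days", plus 30 days after the last start.

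**Baseline label.** Section 8.8 calls October 2021 to September 2022 "the year prior the request for PRAC to review current evidence on NOMAC and CMA". Appendix II lists "Date of request for PRAC assessment by France" as 22/09/2021.

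**Hypothesis.** Tables 1 and 11 expect dose and duration to be lower after the restrictions.

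**The concern.** Two initiation windows of equal length do not give two cohorts equal time in which to accumulate dose. If accrual runs to the end of data, the earlier cohort always has longer. Some of its extra time also lies after the restrictions took effect, so its value is not purely pre-intervention. The resulting shortfall in the post cohort points the same way as the hypothesis. The standardised mean difference, the planned pre/post measure, would not separate it from a real change.

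The baseline label is a second, independent matter. A baseline described as preceding the review in fact falls within it.

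**Working it through.** **Inputs.** Locks from Table 3: Germany 30-09-2023, Belgium 31-12-2023, NAJS 17-11-2023. Windows from section 8.8. Milestone dates from Appendix II. The protocol gives no treatment length, so a range is assumed.

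**1. The plan's own figure.** The windows are indeed equal: 365 and 365 days, or 181 and 181 days.

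**2. Potential follow-up under sections 8.8 and 8.4, 6-month windows.** Follow-up = lock date minus start date, averaged over uniform starts; 1 month = 30.4375 days. Germany, pre: 426 to 606 days, mean 516, and 516/30.4375 = 17.0 months. Germany, post: 61 to 241 days, mean 151, or 5.0 months.

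| Database | Pre (months) | Post (months) |
|---|---|---|
| Germany | 17.0 | 5.0 |
| Belgium | 20.0 | 8.0 |
| Croatia | 18.5 | 6.5 |

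The gap is 12 months everywhere, and a later lock would not change it. In Germany, 1 February to 30 September 2023 (241 days, 7.9 months) of each 2022 starter's potential follow-up lies in the post-intervention period.

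**3. Artefact if prescribing is unchanged.** Let treatment length be exponential with mean m in both cohorts and daily dose constant. Expected exposed time for follow-up f is m(1 - exp(-f/m)). For m = 6 at the mean German follow-ups: 6(1 - exp(-17.0/6)) = 5.65 and 6(1 - exp(-5.0/6)) = 3.39. Averaged over all start dates these become 5.63 and 3.27, a ratio of 0.58. Post/pre ratio of mean exposed time, with simulated SMD (difference in means over the root of the average variance):

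| Mean length (months) | Germany | Belgium | Croatia |
|---|---|---|---|
| 1 | 0.98 (-0.02) | 1.00 (0.00) | 1.00 (0.00) |
| 3 | 0.78 (-0.27) | 0.92 (-0.09) | 0.87 (-0.15) |
| 6 | 0.58 (-0.63) | 0.75 (-0.34) | 0.68 (-0.45) |
| 12 | 0.44 (-1.12) | 0.59 (-0.74) | 0.53 (-0.90) |

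The median, which Table 1 names as the Objective 2 summary, is less sensitive. In Germany it is 2.07 against 2.05 months at m = 3, and 4.15 against 3.02 at m = 6.

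**4. Accrual capped at the window instead.** Mean time to window end = (observed window days - 1)/2.
- 6-month design: (181 - 1)/2 = 90 days = 2.96 months in both cohorts and all databases. The asymmetry vanishes.
- 12-month design, pre: (365 - 1)/2 = 182 days = 5.98 months.
- 12-month design, post, cut at the lock: Germany (242 - 1)/2 = 120.5 days = 3.96 months; Belgium (334 - 1)/2 = 166.5 days = 5.47; Croatia (290 - 1)/2 = 144.5 days = 4.75. No stated lock reaches 31 January 2024.

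**5. Baseline label.** From 22 September to 1 October 2021 is 9 days, so the window follows the request. From the PRAC recommendation (7 July 2022) to 30 September 2022 is 25 + 31 + 30 = 86 days of the 365.

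**The case against.** The best defence is that the sentence on all recorded treatments is the general dose rule, while the pre/post comparison has its own sentence about equal periods, supported by the abstract. On that reading the 6-month comparison is balanced. This stands as a possible reading, but the body of the protocol does not settle it. Sections 8.8 and 8.4 taken literally give the opposite, section 8.1 is silent, and two programmers could reasonably code different analyses. Even the favourable reading leaves the 12-month design unequal on the stated locks.

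Four stronger inferences are tempting and are not supported:

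- *Duration falls by construction everywhere.* In Germany and Belgium, duration comes from the dates of the first treatment's prescription and depends little on the lock. Truncation is plausible mainly in NAJS.
- *The gap is 17 against 5 months throughout.* Those levels are Germany's, under the 6-month windows. They are also potential follow-up; section 8.4 ends follow-up earlier when observation stops.
- *The baseline dating makes dose fall.* It concerns only the 12-month design. If prescribers had already reacted to the review, it would lower the baseline and shrink the contrast.
- *The 1-year contrast can be run nowhere.* Section 8.8 has a 6-month fallback. Table 3 gives the last update's lock, code execution is planned for March/April 2025, and the study period runs to the end of available data, so a later cut cannot be excluded.

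**Conclusion.** The point holds as an unresolved inconsistency with a calculable consequence. Objective 2 fixes no equal per-patient accrual period. Read as sections 8.8 and 8.4 stand, cumulative dose is biased downward after the restrictions in all three databases, with NAJS duration affected secondarily. The size depends on treatment length. In Germany, with the 6-month windows, it runs from negligible at a 1-month mean (ratio 0.98, SMD -0.02) to large at 12 months (0.44, -1.12); Belgium and Croatia show less. These figures assume exponential lengths, constant daily dose, uniform starts, the Table 3 locks and no earlier loss of observation.

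The baseline label is a plain contradiction with Appendix II. The documents do not show whether the label or the dates are wrong.

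**What to change.** - Reconcile the abstract with sections 8.8 and 8.4: accrue cumulative dose over the same per-patient period in both cohorts. Three options work: within the matched 6-month window; to a mirrored cut-off, one year before the lock, for the 2022 cohort; or to a common horizon from index. The mirrored cut-off falls on 31 December 2022 in Belgium and 17 November 2022 in NAJS, so some pre accrual would still lie in the transition period. A common horizon must allow for section 11's note that IQVIA observation ends at the last interaction.
- Apply the same censoring to NAJS duration.
- Make the 1-year contrast in Table 11 conditional on the analysed lock covering the whole post window; otherwise use the 6-month contrast.
- Separately, correct the baseline label or move the window. Section 11 cautions that COVID-19 effects may persist in 2021, so an earlier baseline belongs in a sensitivity analysis.

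The cost is wording and cohort dates, with no new data. The real downside is that a shorter accrual period says less about long-term use.
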